Phase II: 20 additional subjects coming to the COVID-19 clinic at Baylor College of Medicine for treatment of long-term neuromuscular complications due to severe COVID-19 infection. Patients will begin the study after indication of muscle weakness, muscle atrophy, fatigue, or neuromyopathy due to prolonged immobilization (i.e. at home or in the hospital) for COVID-19. This assessment can be performed by a critical care and pulmonary specialist at the BCM COVID-19 Clinic. This is a proof of concept randomized control trial (RCT) study for recovery. The entire cohort will receive daily, at-home electrical stimulation in the lower extremities (e.g. gastrocnemius, tibial anterior muscle) for up to 1 hour to aid in recovery from neuromyopathy complications due to prolonged immobilization. Participants will be randomized to intervention (IG) or control group (CG). EE therapy will be provided using a portable EE device. The EE device will be functional for IG and non-functional for CG. The primary outcomes include between group difference and change from the baseline in muscle endurance, muscle strength, lower extremity tissue oxygen saturation, neuropathy, and muscle atrophy. The patients will take the device home up to 4 weeks and will be screened once a week at Baylor College of Medicine McNair Campus for neuromuscular evaluation. The control group will be unblinded after the 4 weeks are completed with the option of extending to 4 additional weeks by switching to an active device.

Inclusion Criteria:

Phase I: Age: Adults age 18 years or older Disease status: COVID-19 test positive Critically ill requiring care in the hospital.

Phase II: Age: Adults age 18 years or older Patients must have been previously bedbound or immobilized due to COVID-19 infection Patients with muscle pain, muscle weakness, muscle atrophy, and/or neuromyopathy in the lower extremities Patients will have to be alert and conscious to sign the consent form.

Exclusion Criteria:

Subject has a demand-type cardiac pacemaker, implanted defibrillator or other implanted electronic device Active wound infection Below the knee amputations Based on the clinicians decision whether the patient is eligible for the study.

F2. Procedure

Phase I:

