The researchers will take digital photographs /videos throughout the study. This is done using a special camera for tissue oxygen detection and visual images. This method is non invasive and does not cause any harm to the patient. **We will blur the face out in the photographs/videos. We will only use videos and photos for scientific presentations or scientific publications.

Phase II:

Patients will begin the study after incidence of muscle loss, muscle weakness, muscle pain, or neuromyopathy due to prolonged immobilization for COVID-19. This assessment will be performed by a critical care and pulmonary specialist at the BCM COVID-19 Clinic.

The protocol will consist of 4 weeks of lower-extremity electrical stimulation. This modality will consist of home-based therapy, meaning that the patient will take the device home and attend the clinic once a week for screening and assessment of therapy.

The protocol will be performed as the following description: This trial will have 20 patients divided in two groups. Group 1 (intervention, n=10): Will receive an active Tennant Biomodulator. Patients assigned the active device (active group; Group 1) at their initial visit (baseline) will only have 4 weeks of study participation (which includes 5 visits: Baseline (week 0), Visit 1 (Week 1 of at-home therapy), Visit 2 (Week 2 of at-home therapy), Visit 3 (Week 3 of at-home therapy), Visit 4 (Week 4 of at-home therapy). After 4 weeks, the patients will turn back the electrical stimulation device to the research staff.

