Group 2 (control, n=10): Will receive an inactive Tennant Biomodulator for 4 weeks. The control group will have the option to receive an active device after their 4 weeks visit. Should they agree, they would receive at-home therapy for another 4 weeks and come to the clinic for up to two additional visits for assessment. If the subject agrees to receive the active device at the 4th week visit (visit 4), then they will only be required to attend the clinic for one more visit (visit 5). For subjects in this group that were previously enrolled (i.e. Visit 4 completed), they will be contacted to be unblinded and confirm agreement/reconsent to have another 4weeks of study participation with an active device. They will have 2 additional visits (visit 5 and Visit 6). Visit 5 will consist of the same procedures and one hour of stimulation than visit 4, and the subject will receive an active device to take for additional 4 weeks and come back to the clinic for a final assessment (Visit 6). Visit 6 will consist of the same procedures and one hour of stimulation the subject will return the active device at their last visit (either Visit 5 or Visit 6 depending on the conditions listed above).

Group 2 will consist up to 7 visits total with possible phone calls in between. The patient will be compensated \$50 per inperson, clinic visit (total \$350), with free parking. Payment will only be available for subjects who participate in Part II.

During Visit 1, Visit 2, Visit 3, the the research staff will turn the Tennant Biomodulator PRO® on for 5 minutes and measure any changes in muscle strength, endurance, and blood flow after the therapy.

During Baseline, Visit 4, Visit 5, Visit 6, the research staff will turn the Tennant Biomodulator PRO® on for one hour and measure any changes in muscle strength, endurance, and blood flow after the therapy. Once the Baseline is over, the patient will take the Tennat Biomodulator® home and will be instructed to turn it on for one hour every day for four weeks.

Any study visits may include the following assessments in addition to electrical stimulation: 1) Questionnaires (pain, weakness, sleep, quality of life, frailty, depression, life and space, beck anxiety scale, Katz-daily living, fatigue) 2) Musculoskeletal assessments (non-invasive surface electromyography, vibration perception threshold, leg circumference measurement, ankle strength test) 3) Vascular assessments (non-invasive Near infra-red spectroscopy)

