P-values of 0.05 or less will be considered statistically significant based on a two-sided test unless otherwise noted. All variables will be tabulated descriptively at each scheduled time point (baseline and discharge date). For each continuous variable, the analyses will include the mean, standard deviation, minimum and maximum. For each categorical variable, the summary will include frequencies and percentages. Each variable will be analyzed using all available data. Baseline variables will be summarized using descriptive statistics. We assume that a successful intervention is also helpful to maintain subjects muscle mass, reduce neuromyopathy signs and increase venous return flow. The measured parameters (e.g. muscle circumference, sEMG, kent imaging, doppler, etc.) should change substantially from baseline to the end of the intervention. For example, the EMG amplitude values should show increased voltages. Next, for all continuous variables, pre-treatment scores will be regressed on post-treatment scores to form residualized change scores (e.g. sEMG, VPT, dynamometer, etc). Correlations will then be generated among these scores to determine whether changes in sEMG factors are related appropriately with increases in (clinically assessed) functional capacities and self-report measures of activities. ANOVA test will be used to examine significant difference between patients with severe risk factors for prolonged ICU stage (e.g. age, BMI, cardiovascular morbidities). Moderator effects will also be examined for exploratory purposes. Using gender as an example, mixed design ANOVAs will be conducted to determine whether mobility factors change over the course of treatment at different rates or with different patterns for men and women. Additional analyses will test whether changes in muscle strenght and neuropathy (e.g. VPT and dynamometer assessement at time of discharge).

Section H: Potential Risks/Discomforts

H1. Potential Risks/Discomforts

Describe and assess any potential risks/discomforts; (physical, psychological, social, legal, or other) and assess the likelihood and seriousness of such risks:

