activation. The device is used to reduce pain. However, the proposed treatment may assist in preventing or improving hospital-acquired Weakness because of prolonged hospital stay . In addition, the participation in this study may help the investigators better understand how COVID19 may impact cause myopathy and neuropathy and how to best help these patients to recover from prolonged hospital-stay .

Primary outcomes include neuropathy (assessed using VPT test); muscle function (assessed using sEMG), and tissue oxygenation (assessed using Kent Imaging). Secondary outcomes include weakness (assessed using dynamometer); muscle atrophy (assessed by weight loss as well as measuring ankle, calf, and thigh circumference); venous return flow (Doppler US [optional]); frailty (frailtymeter [optiona]); hospital length of stay (patient medical record); and major adverse events (patient health record). The primary and secondary outcomes will be assessed at baseline (if feasible) and on biweekly basis up to 4 weeks or hospital discharge, whichever came first. Appropriate mixed models (linear for continuous or Generalized Estimating Equations (GEEs) for non-continuous or non-parametric variables) will be used to test the intervention effect for each of the primary (e.g., tissue perfusion, tissue oxygen delivery, neuropathy severity, and myopathy incident) or secondary (e.g., frailty, weight loss, MAE, etc) outcomes.

Also, participation may help the investigators design a practical assessing method to identify the impact of neuromyopathy in the hospital setting. This may allow physicians to provide personalized care by monitoring muscle loss and limb complications caused by prolonged hospital length of stay.

Describe potential benefit(s) to society of the planned work.

As described above, this type of work may allow physicians to provide more personalized care for hospitalized patients in need of physical therapy for continuous and prolonged periods, specially when having a severe illness that includes medical staff risk contact.

Do anticipated benefits outweigh potential risks? Discuss the risk-to-benefit ratio.

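### Does Phase II mix 5-minute and one-hour readings in its test of the treatment effect?

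*Combined protocol and SAP*

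**What the plan says.** Section F2 (Procedure, Phase II) gives patients a device to use at home for four weeks and asks them to "attend the clinic once a week for screening and assessment of therapy". At Visits 1, 2 and 3 staff turn the device "on for 5 minutes and measure any changes in muscle strength, endurance, and blood flow after the therapy". At Baseline and Visits 4, 5 and 6 they turn it "on for one hour and measure any changes in muscle strength, endurance, and blood flow after the therapy". The three measures are worded identically and only the session length differs. Section F1 says "The EE device will be functional for IG and non-functional for CG".

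The analysis is described in three places. F1 sets the Phase II primary outcomes as the difference between arms and the change since baseline in endurance, strength, tissue oxygen saturation, neuropathy and atrophy. G2 names two time points, baseline and discharge, expects the measures to have moved by the time the intervention ends, and adds "Each variable will be analyzed using all available data". The outcome paragraph in Section I has outcomes "assessed at baseline (if feasible) and on biweekly basis up to 4 weeks or hospital discharge" and says that mixed models or GEEs "will be used to test the intervention effect for each of the primary" and secondary outcomes. It also ranks strength differently from F1: "Secondary outcomes include weakness (assessed using dynamometer".

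None of these places says whether the reading before the session, the reading after it, or the difference between them is modelled, or which weekly visits contribute.

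**The concern.** Session length is tied to visit: 60 minutes, then 5, 5 and 5, then 60. A functional device can produce an acute response and a non-functional one should not. A shorter session could therefore lower the reading at Visits 1 to 3 in the intervention arm alone. In a table of within-session changes that would look like a dip and a recovery in treated patients whose condition had not changed.

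The model in Section I is the only one named for the intervention effect. Its schedule, read as every two weeks, picks out Baseline, Visit 2 and Visit 4, that is one hour, 5 minutes, one hour. Together with G2's use of all available data, this could be taken to mean that unlike exposures are modelled as one repeated measure. At stake would be a diluted estimate of the one-hour effect or, if post-session values were used, a biased comparison of arms at Week 2.

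**Working it through.** The plan gives no power calculation and no acute effect size, so there is no figure to reproduce. The check asks which analyses session length could distort.

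**Inputs from the documents.** Sessions of 60 minutes at Baseline and Visit 4 and 5 minutes at Visits 1 to 3 (F2), a ratio of 60/5 = 12. Device active in one arm only up to Visit 4 (F1, F2). Ten patients per arm (F2).

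**Assumptions.** A is the acute effect of one hour in the active arm, constant over the four weeks. kA is the effect of 5 minutes, with k from 0 to 1. There is no acute effect in the control arm and no cumulative effect, so anything other than zero in a change or trend over time is artefact.

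**Active minus control, within-session change or post-session value,** at Baseline and Visits 1, 2, 3, 4: A, kA, kA, kA, A.

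| Analysis | Formula | k = 0 | k = 0.5 | k = 1 |
|---|---|---|---|---|
| Baseline to Visit 4 | A − A | 0 | 0 | 0 |
| Linear trend, five visits | (−2A − kA + 0 + kA + 2A)/10 | 0 | 0 | 0 |
| Linear trend, Baseline, Visits 2 and 4 | (−A + 0 + A)/2 | 0 | 0 | 0 |
| Mean change from Baseline, Visits 2 and 4 | [(k−1)A + 0]/2 | −0.50A | −0.25A | 0 |
| Mean change from Baseline, Visits 1 to 4 | [3(k−1)A + 0]/4 | −0.75A | −0.375A | 0 |
| Linear trend, Visits 1 to 4 only | 1.5(1−k)A/5 | 0.30A | 0.15A | 0 |
| Average level over five visits | (2+3k)A/5 | 0.40A | 0.70A | A |

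The last row is a level, not a change, so its reference value is A. If the modelled reading is taken before the session starts, that visit's session length does not enter it and every analysis is unaffected.

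**Which rows does the plan select?** F1 asks for change since baseline and G2 for the two ends of treatment. In Phase II the nearest equivalent is Baseline against Visit 4, the first row. Section I does not state time terms, so it selects neither the zero rows nor the others. No section asks for an average of the group difference across all visits with Baseline included, which is what the last row needs. Nor does F1 or Section I list the within-session change as a Phase II outcome. The aim devoted to immediate effects, Aim 1 in F2, belongs to Phase I.

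**The schedule.** The wording in Section I ends at hospital discharge, which is a Phase I event because Phase II patients attend as outpatients. The frequency term can also mean twice a week. Mapping it to Baseline, Visit 2 and Visit 4 is therefore one reading among several.

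**The case for a change.** The best case for acting is that the facts in F2 are not in dispute and the measures overlap with the F1 primary outcomes. Silence on the modelled reading also leaves the choice open until the data are in hand. Phase I Aim 1 itself takes optional readings at 30 and 60 minutes, so the investigators regard acute response as depending on time. If the session lengths were chosen on purpose, that is more reason to analyse them apart, and two or three sentences would do it.

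Part of this stands. The reading and the visits are not named. Anyone who tabulated within-session change by visit as one time course would be comparing unlike sessions. A joint group-by-visit test on those changes could also respond to session length, because the pattern A, kA, kA, kA, A is not flat when k differs from 1.

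The step from there to a flawed model does not stand. It needs the analyst to choose within-session or post-session readings, to include Visits 1 to 3, and to average them with the one-hour visits. It also needs a 5-minute effect that differs from the one-hour effect, on which the documents are silent. Using all available data is a rule about not discarding observations and does not require unlike ones to be pooled. A shift from resting for an hour rather than 5 minutes between tests would be common to both arms at a given visit and would cancel in the comparison. Losses of power at an assumed effect size carry little weight, since G1 sets the sample by convenience and claims no power.

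**Conclusion.** The different session lengths are real, but they do not damage any analysis that the plan commits to. For Baseline to Visit 4 the artefact is exactly zero for any k, provided the acute effect of an hour is stable over the four weeks. For pre-session values, session length does not enter at all. A linear trend over complete visits is also free of it, although with missed visits the cancellation need not be exact. The largest distortion in a change from Baseline, −0.75A at k = 0, belongs to an average that the plan does not specify, and both A and k are assumptions.

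What is left is missing detail about the reading and the visits. An analyst would ordinarily use pre-session values, or Baseline against Visit 4, for the four-week comparison, and would describe within-session changes separately by session length. Visit number fixes session length, so the data can be separated without further collection. In a pilot of 10 per arm, no change to the plan is needed on this account.

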Phase II (recovery): Moreover, we also propose to examine the effectiveness of daily use of electrical stimulation therapy to recover from the long-term neuromuscular side effects of prolonged immobilization in patients who were bedbound due to COVID-19. These effects include lower extremity critical illness myopathy and neuropathy. Lengthened periods of immobilization decreases muscle activity provoking atrophy, weakness, and pain. We hypothesize that electrical stimulation will help to increase muscle fiber activation and nerve conductivity, thus, help in recovery of the neuromuscular condition.

Section E: Protocol Risks/Subjects

E1. Risk Category

Category 1: Research not involving greater than minimum risk.

E2. Subjects

Gender:

Both

Age:

Adult (18-64 yrs), Geriatric (65+ yrs)

Ethnicity:

All Ethnicities

Primary Language: English

Groups to be recruited will include: Patients

Which if any of the following vulnerable populations will be recruited as subjects?

Cognitively impaired

Vulnerable populations require special protections. How will you obtain informed consent, protect subject confidentiality, and prevent undue coercion?

Due to no visitation, the consent will be done over the phone by the physician with a legal representative of the patient. Two nurses will be present during the call and the consenting will be done by the physician following current consenting procedures with other ongoing studies in the hospital. This study has minimal risks for the patient, all notes will be added to the consent form based on the call. If patient is able to give verbal consent will be singed physically.

For patients who lack the capacity to consent, the investigator/designee may explain the study to the legally authorized representative by phone. The discussion will be documented in the subject's medical record or research chart. Two copies of the unsigned consent form will be sent to the subject/legal representative with instructions for completion of the signature page and assent (if applicable). Signatures will be obtained according to standard Baylor IRB regulations. The subject will be told to keep one form and returned the other to the investigator by mail, email, or fax. The Baylor Investigator/designee will sign the consent form when returned from the subject. The signed consent form will be maintained in research records.

E3. Pregnant woman/fetus

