Aim1 (to understand mechanism of action): Examine immediate benefit of lower extremity EE to improve venous return flow, tissue oxygenation, and muscle activation (short term benefit). In this study, we will recruit a convenient sample of 20 hospital patients diagnosed with COVID-19 (short-term benefit).

Optional: Subjects will be assessed using Doppler ultrasound and near infrared imaging (Kent Imaging System) at pre-, 30min, 60min, and 30min post-treatment (after stopping of EE device). Lower extremity muscle activation will be assessed by using sEMG (electromyography).

Patients will begin the study after being admitted to the hospital no more than 48 hours.

Aim 2 (to examine effectiveness): Examine effectiveness of daily use of EE to treat CINM, and other associated major adverse events (MAE) including deep vein thrombosis (DVT), cardiovascular events, and death. Participants will receive standard of care plus adjunctive daily EE therapy using an FDA approved bio-electric stimulation technology (BEST) platform (Tennant Biomodulator® PRO, AVAZZIA, Inc) during the entire length of stay in hospital. The device will be provided by the research staff.

We will assess incidence of neuropathy and myopathy during hospital discharge or 2 weeks, whichever comes first. Neuropathy severity will be quantified using vibratory perception threshold (VPT) test. Myopathy will be assessed by measuring changes in calf muscle circumstance, weight change from pre-hospital admission, and sEMG. In addition, we will determine weakness using foot dynamometer and a validated frailty meter. Length of hospital stay and MAE (documented via electronic health record) will be tracked for planning of future studies. Both extremities will have all measurements and 1 hour electrical stimulation therapy at baseline. Daily treatment will performed up to 3 times per day, but no more than 1 hour in total.

Daily electrical stimulation will be administered by a nurse/staff involved in the hospital care. A chart will be signed to register each therapy performed and will include a log of day and time of device application.

Both electrical stimulation and EMG devices will have disposable pads, after usage they will be discarded. For the Devices they will be placed inside a plastic bag that will be disposed inside the room before exiting and sanitized (wipes) based upon hospital protocols.

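### In Phase II the plan does not say whether the outcome value is read before or after the visit-day stimulation, so the arm comparison can mix the immediate effect with the effect of four weeks of use

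*Combined protocol and SAP*

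**What the plan says.** The protocol asks two questions of the device. Section F2, Phase I, Aim 1 concerns a single session: "Examine immediate benefit of lower extremity EE to improve venous return flow, tissue oxygenation, and muscle activation (short term benefit". Section D, Phase II concerns weeks of use, on the hypothesis that stimulation will "help in recovery of the neuromuscular condition".

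The Phase II visit procedures in Section F2 are:

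- **One-hour visits (Baseline and Visits 4, 5 and 6).** Staff are to "turn the Tennant Biomodulator PRO® on for one hour and measure any changes in muscle strength, endurance, and blood flow after the therapy".
- **Visits 1 to 3.** Staff "will turn the Tennant Biomodulator PRO® on for 5 minutes and measure any changes in muscle strength, endurance, and blood flow after the therapy".
- **Home use.** The patient "will be instructed to turn it on for one hour every day for four weeks". Nothing is said about home use on a clinic day.

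Section F1 lists endurance, strength and tissue oxygen saturation among the primary outcomes. Section I says: "Primary outcomes include neuropathy (assessed using VPT test); muscle function (assessed using sEMG), and tissue oxygenation (assessed using Kent Imaging"; it makes dynamometer strength secondary. The control device is non-functional (Section F1). Group 1 returns the device after week 4 and has no later visit (Section F2).

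Section G2 (residualized change scores) and Section I (mixed models or GEE) give the analysis. Neither names the reading that supplies the outcome value.

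For Phase I, Section F2 says: "Both extremities will have all measurements and 1 hour electrical stimulation therapy at baseline". It does not give the order of the two. It does require a log of the day and time of each application.

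**The concern.** The protocol itself expects a session to move tissue oxygenation and muscle activation at once, and both are primary outcomes for the effect of daily use. The visit procedures also look for changes in strength and endurance after a session. The sham arm does not remove an immediate effect, because it has none to cancel.

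If the end reading follows a session and the baseline reading does not, a purely short-lived response would look like four weeks of recovery. With the reverse pairing, part or all of a real lasting effect would be subtracted. No off-treatment reading in Group 1 could settle the matter later. The order of reading and stimulation cannot be repaired once the data are collected.

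**Working it through.** **Inputs.** Phase II has 10 patients per group (Section F2) and two-sided testing at 0.05 (Section G2). Sessions last 60 minutes at Baseline and Visit 4 and 5 minutes at Visits 1 to 3 (Section F2). The documents give neither the size of an immediate effect nor any SD, so both are assumed below. Section G1 sets the sample size by convenience, so there is no planned power figure to reproduce.

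**Step 1: what each pairing estimates.** Write each term as active minus control: c is the lasting effect, a0 and a4 are the immediate effects at Baseline and Visit 4, and r is the residue of the last home session in a pre-session Visit 4 reading. For a simple change from baseline:

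| Baseline reading | Visit 4 reading | Between-group difference in change | With c = 0, r = 0, a0 = a4 = 0.8 SD |
|---|---|---|---|
| before session | before session | c + r | 0 |
| after session | after session | c + a4 − a0 | 0 |
| before session | after session | c + a4 | +0.8 SD |
| after session | before session | c + r − a0 | −0.8 SD |

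The plan permits all four. Three further cases matter:

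- If the immediate effect wanes with use (a0 = 0.8, a4 = 0.4, c = 0), the after/after pairing gives 0.4 − 0.8 = −0.4 SD.
- If there is a real lasting effect (c = 0.8, a0 = 0.8, r = 0), the after/before pairing gives 0.8 − 0.8 = 0 and hides it.
- A comparison of the arms on the post-session Visit 4 reading alone gives c + a4.

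If baseline enters as a covariate with slope b instead of being subtracted, the after/after pairing leaves a4 − b·a0. With equal immediate effects that vanishes only when b = 1.

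**Step 2: illustration for the before/after pairing.** Assume c = 0, an SD of 8 points for the analysed score, and an immediate effect of a points in every active-arm end reading and in no baseline reading. The noncentrality of the two-sample t-test is a / (8 × √(2/10)) = a / 3.578, with 18 degrees of freedom and critical value 2.101.

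| a (points) | a / SD | Noncentrality | Chance of p≤0.05 |
|---|---|---|---|
| 3 | 0.375 | 0.84 | 12.5% |
| 5 | 0.625 | 1.40 | 26.3% |
| 8 | 1.000 | 2.24 | 56.2% |

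The nominal rate is 5%. It is kept when the bias in Step 1 is zero.

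**Step 3: the change of session length.** If post-session readings from all visits enter one repeated-measures model, the Visit 3 to Visit 4 step contains (one-hour effect − 5-minute effect). With an assumed 0.8 SD at one hour, the false step is 0.8 − 0.4 = 0.4 SD if 5 minutes gives half the effect, and 0.8 SD if it gives none.

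**The case against.** The strongest reply is that measuring a change after therapy presupposes a reading before it, so the data needed to separate the two effects may already be planned. This stands in part. A pre-session reading may well exist, but no section makes it the outcome value, and it could still follow a home session that day.

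A second reply is that Baseline and Visit 4 have the same one-hour session, so post-session readings at both would cancel. This stands for a simple change score if the immediate effect is the same at first use and after four weeks. The plan neither states nor checks that.

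Third, the percentages apply to one pairing, which no section prescribes. That is correct, and they are offered only on that footing.

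Fourth, this is a convenience-sample pilot. That lowers the stakes. Even so, Section G1 claims proof-of-concept effectiveness and Section G2 tests at 0.05, so a session effect mistaken for recovery could misdirect the next trial.

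A reader might go further and infer that end readings in both phases follow stimulation. The documents do not support this for Phase I: they are silent on order there, and the application log allows a check. Nor do they say that Phase II patients stimulate at home before attending, or whether the clinic hour counts as that day's hour.

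**Conclusion.** The point holds for Phase II and should be acted on. The one reading order that is described places strength, endurance and flow readings after stimulation. The outcome value is not defined, and session length changes between Visits 3 and 4. On a simple change score the bias ranges from zero (matched readings, under the conditions above) to plus or minus the full immediate effect (mixed readings). The 12%, 26% and 56% figures rest on an assumed SD, assumed effects and an assumed pairing. They are not expected error rates for this trial.

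A reader might infer that lasting recovery cannot be separated from the short-term response at all. That is too strong: pre-session readings at both visits would largely separate them, and the plan does not rule these out. The scope is also limited. The concern applies to tissue oxygenation, sEMG, strength, endurance and flow. It bears little on length of stay, major adverse events or weight, and Aim 1 does not name vibration perception threshold or limb circumference as immediate-effect measures. For Phase I the defect is only that the timing is unstated.

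**What to change.** - **Phase II readings.** At Baseline and each follow-up visit, take the outcome readings before the clinic session. Use only these in the Section G2 and Section I analyses of the intervention effect.
- **Post-session readings.** Analyse them only as the immediate effect (within-visit change by arm), without pooling 5-minute and one-hour sessions.
- **Phase I.** Take the baseline readings before the first stimulation. Use the existing application log to report the time since last stimulation at the end reading.
- **Home use in Phase II.** Record the time of the last home session before each visit.
- **Sensitivity analysis.** Use both times to examine whether the result depends on how recently stimulation was given.

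The cost is a new order of procedures on assessment days and one extra recorded time in Phase II. No visit is added, and no change to the amount or schedule of stimulation is proposed.
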